3.1 Subgroups

Subgroups will be formed for the analyses for the FAS or SAF depending on the parameters under consideration to explore the consistency of treatment effects and safety profiling between the subgroups and the overall population.

In general, subgroups will be defined based on baseline information. In this study, since we have a run-in phase to test patients' tolerability to the study drugs before they can enter the double-blind phase, we have defined two baselines ([Section 4](#)): the run-in baseline and the double-blind baseline. Subgroups may be formed using one of these baselines according to their analysis purposes.

In [Table 3-1](#), we have listed all subgroups defined for this study and the ways to derive them. In different analysis, such as efficacy analysis or safety analysis, a different subset of them will be selected. Also note that only important parameters or variables in these analyses may have subgroup analyses. The details about the parameters having subgroup analyses will be presented in the corresponding sections below. Also, additional subgroups may be formed later for regional or country-wise analyses per request for exploratory purposes.

Table 3-1 Specification of subgroups

Subgroup	Method of Derivation	Disposition /Background & demo. /Exposures	Efficacy (Primary and secondary)	Health economics (KCCQ and EQ-5D only)	Safety
Age groups: <65, ≥65; <75, ≥75 years	Screening	x	x	x	x
Gender	Screening	x	x		x
Race (Caucasian, Black, Asian, Other)	Screening	x	x		x
Region *	Derived (pooled countries or country), using	x	x	x	x

	Screening data				
Diabetic at baseline (yes/no)	Randomization (Derived)		x	x	
Baseline LVEF ≤ median, >median	Screening	x	x		
Atrial Fibrillation based on ECG at baseline: yes/no	Randomization		x	x	
Atrial Fibrillation based on prior history at baseline: yes/no	Randomization		x	x	
Baseline NT-proBNP: ≤ median and > median	Screening		x	x	
SBP ≤ median, >median	Screening		x		
Use of Aldosterone antagonist at baseline: yes/no	Randomization (Derived)		x	x	
ACEi intolerant: yes/no	Screening		x		
Baseline eGFR (<60 vs ≥60 mL/min/1.73 m ²)	Randomization (Derived)		x		
NYHA classification at baseline I/II vs III/IV	Randomization		x		
UK				x	

* **North America:** USA, Canada

Latin America (including Central America): Argentina, Brazil, Colombia, Guatemala, Mexico, Peru

Western Europe: Austria, Belgium, Denmark, Finland, France, Germany, Greece, Italy, Netherlands, Norway, Spain, Sweden, Switzerland, UK

Central Europe: Bulgaria, Croatia, Czech Republic, Hungary, Poland, Rep. of Slovakia, Romania, Russia, Serbia, Turkey, Slovenia

Asia/Pacific and other: Israel, South Africa, Australia, China, India, Japan, Rep of Korea, Philippines, Singapore, Taiwan.

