3.2 Rationale of study design

3.2.1 Target study population and rationale

The study population will consist of patients ≥ 50 years of age with a LVEF $\geq 45\%$ and evidence of structural heart disease (LAE or LVH), current symptoms of HF (NYHA class II-IV) and prior symptoms of HF requiring treatment with diuretic therapy. In addition, patients will have at least one of the following: (1) a hospitalization for HF within 9 months prior to enrollment and NT-proBNP >200 pg/ml for patients without AF or >600 pg/ml for patients with AF on Visit 1 ECG; **OR**, (2) NT-proBNP >300 pg/ml for patients not in AF or >900 pg/ml for patients in AF on Visit 1 ECG. These criteria should identify the target HFpEF population at risk for major CV events.

Structural heart disease (LAE and LVH) is a key diagnostic criterion for HFpEF in the most recent guidelines ([McMurray et al 2012](#)). Left atrial (LA) size (an integrative measure of left ventricular diastolic pressure) is independently associated with an increased risk of morbidity and mortality ([Zile et al 2011](#)). Including either LAE or LVH will help ensure a diagnosis of HFpEF. The EF lower boundary at 45% was selected to include a wide spectrum of patients for whom no proven therapy is currently available. Prior HF hospitalization and elevated NT-proBNP were the strongest independent predictors of mortality and subsequent HF hospitalization in the I-PRESERVE study ([Solomon et al 2007](#), [Komajada et al, 2011](#)). Patients with baseline AF are required to have higher NT-proBNP levels, as AF is strongly associated with higher levels of NT-proBNP ([McKelvie et al 2010](#)). The number of AF patients will be limited to approximately one third in the current study (based on the Visit 1 ECG) so that the proportion of patients with AF in the study will be representative of the HFpEF population ([Massie et al 2008](#), [Steinberg et al 2012](#), [West et al 2011](#)).

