9.3.1.3 Subgroup analysis

A full set of subgroups will be performed for subgroup analysis for the primary endpoint and its components, as outlined at [Section 3](#).

Subgroup analyses will be performed for the FAS. To explore beneficial effects in subgroups or homogeneity of beneficial effects among subgroups, the estimated rate ratio, two-sided 95% confidence interval, and within subgroup p-value and p-value for the test for the treatment-by-subgroup interaction will be provided for each of the subgroups based on the proportional rates model in which treatment, subgroup, and treatment-by-subgroup are included as fixed-effect factors. Positive findings from these subgroup analyses have to be interpreted with caution since there is a non-negligible chance of false positives. Rate ratios from each subgroup will be graphically displayed using a forest plot.

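### Whether the treatment effect varies with baseline LVEF is tested only through a median split; adding a pre-specified continuous interaction would recover about a third of the information on a graded effect

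*SAP*

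**What the plan says.** SAP Table 3-1 lists the efficacy subgroups. LVEF, taken from screening, is "Baseline LVEF ≤ median, >median". NT-proBNP and SBP are also cut at their sample medians ("Baseline NT-proBNP: ≤ median and > median" and "SBP ≤ median, >median"), eGFR is cut at 60, and age has two separate cuts: "Age groups: <65, ≥65; <75, ≥75 years".

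For the primary endpoint and its components, SAP 9.3.1.3 fits a "proportional rates model in which treatment, subgroup, and treatment-by-subgroup are included as fixed-effect factors" and states that a "p-value for the test for the treatment-by-subgroup interaction will be provided for each of the subgroups". SAP 9.3.2.6 carries the approach over to the secondary endpoints. Protocol 9.4.2.4 uses the same cuts and the same kind of model.

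Two places in the SAP come near a continuous analysis but do not supply one. The time-dependent SBP models in 9.3.1.2 adjust for SBP to see whether it drives the effect and state no treatment interaction. The same section allows further supportive analyses but names none.

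The SAP describes the subgroup work as exploring consistency, makes no multiplicity adjustment (3.2), and asks that positive findings be read with caution (9.3.1.3).

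**The concern.** LVEF by echocardiography is an entry requirement, so a numerical value should exist for essentially every patient. The protocol says "The EF lower boundary at 45% was selected to include a wide spectrum of patients" (3.2.1), so the trial deliberately covers a range of ejection fractions.

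A median split can say only whether the lower and upper halves differ. It treats a patient just above 45% like one just below the median, and it cannot describe how the effect changes along the scale. If the effect is graded, the split has less power to show it.

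Two things are at stake. A null split interaction could be read as evidence of consistency when the test had little chance of showing otherwise. And a gradient examined only after unblinding would be post hoc, although it could have been planned at almost no cost.

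**Working it through.** **1. Reproducing the plan's figure.** The documents give no power for any interaction test, so the check starts from the primary power table (SAP Table 13-1). Inputs from SAP 13.1 and protocol 5.2 and 9.7.1: 4600 patients, 1:1; shared gamma frailty with shape 0.193; control rates of 0.09 per year for a first event and 0.04 for CV death; 29 months of uniform accrual and 26 months minimum follow-up; one-sided alpha 0.025. The documents do not say over what period the annual rates are averaged; about 3.2 years was assumed. With 3000 simulated trials per row, analysed by LWYY with robust variance:

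| HR death / RR HF hosp. | Events, plan | Events, simulated | Power, plan | Power, simulated |
|---|---|---|---|---|
| 0.9 / 0.7 | 1847 | 1839 | 0.95 | 0.954 |
| 0.9 / 0.75 | 1882 | 1878 | 0.85 | 0.837 |
| 1.0 / 0.7 | 1846 | 1842 | 0.94 | 0.941 |
| 1.0 / 0.75 | 1885 | 1880 | 0.82 | 0.828 |

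The design is reproduced, so the same simulation can carry an interaction.

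**2. Information kept by a split.** If the log rate ratio is linear in the covariate, the information kept by a two-level factor, relative to the linear term, is the squared correlation between indicator and covariate. For a normal covariate with a proportion p below cut c (in SD units from the mean), this is φ(c)² / [p(1 − p)].

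- Median: (1/2π) / 0.25 = 2/π = 0.637, a loss of 36.3%.
- Off-median cuts: loss of 38% at 40/60, 42% at 30/70 and 51% at 20/80.
- Normal LVEF truncated at 45%, assumed mean 50 to 60 and SD 6 to 10: loss at the median of 34.2% to 36.1%.
- Other shapes cut at the median: 25% (uniform) and 52% (exponential).
- A true step at the median: the split loses nothing. The squared correlation is symmetric, so for a normal covariate it would then be the linear term that loses 36.3%.

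**3. What that means for power.** Two-sided 0.05, normal covariate, power = Φ(z√0.637 − 1.96):

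- 80% with the continuous term (z = 2.80): Φ(2.80 × 0.798 − 1.96) = Φ(0.27) = 61%.
- 90% (z = 3.24): Φ(3.24 × 0.798 − 1.96) = Φ(0.63) = 73%.

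These starting powers are reference values only; the plan does not claim either.

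**4. Check in simulated LWYY trials.** Both interaction models were fitted to the same 1000 trials per setting. Rates here were averaged over 3.0 years, giving about 1764 events, so absolute powers are slightly low. LVEF was drawn from a normal with mean 57.5 and SD 8, truncated at 45:

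| Assumed log-RR slope per SD | Mean z, continuous | Mean z, split | Loss = 1 − (ratio of z)² | Power, continuous | Power, split |
|---|---|---|---|---|---|
| 0.15 | 1.573 | 1.264 | 35.5% | 35% | 24% |
| 0.20 | 2.105 | 1.700 | 34.8% | 57% | 38% |

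Over slopes of 0.10 to 0.20 and three covariate shapes (normal, truncated LVEF, and LVEF rounded to 5 points), the loss was 35% to 38%. The slope is an input to the patient-level model and shrinks on the LWYY scale: with a standard error near 0.070, a mean z of 2.105 implies about 0.147. The plan's own table shows the same shrinkage, where inputs of 0.7 and 0.9 give an LWYY ratio of 0.778.

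**5. Equivalent sample size.** 4600 × 0.637 = 2,928 and 4600 × 0.658 = 3,027. For a linear gradient, the split performs like a continuous test on about 2,930 to 3,030 of the 4,600 patients.

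**The case against.** The strongest reply is that this is a preference, not a fault. The protocol and SAP agree on the cuts, which were set in advance. The analyses are labelled exploratory, and no alpha or stopping rule depends on them. A forest plot with interaction p-values is a recognised way to show consistency. All of that stands, and it is why the point ranks as an optional improvement.

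Several stronger readings are tempting but not supported:

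- *The median split is the weakest test available.* For a normal covariate with a linear gradient, the median is the most efficient two-level cut; every other cut in the working loses more. The loss comes from dichotomising, not from where the cut is placed.
- *A third is lost for all five covariates.* The figure was worked out for LVEF. The eGFR cut at 60 and the age cuts at 65 and 75 need not fall near the median, and NT-proBNP has its own shape, with entry thresholds that differ threefold by AF status.
- *Effect modification by LVEF is a main question of the trial.* Protocol 3.2.1 gives a reason for the eligibility limit, not a hypothesis that the effect varies. No objective in protocol 2.1 to 2.3 concerns it; the only subgroup named in an objective is ACEI-intolerant patients.
- *The continuous test would settle the matter.* At the slopes simulated its power is 35% or 57%, so a null result would be inconclusive under either method.

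Two further cautions hold. LVEF is a local reading, and only about 1200 qualifying echocardiograms go to a core laboratory (protocol 6.6.4). Replacing the categorical tests everywhere would not be cheap: five covariates on the primary and four secondary endpoints is 25 models, or 35 with the two primary components, and some are not LWYY models.

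**Conclusion.** The concern holds for LVEF on the primary endpoint. The only planned test of effect modification by ejection fraction is a median split, and under roughly linear modification it gives up about 34% to 38% of the information that a continuous term would use.

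That size rests on assumptions the documents cannot confirm: the shape of the gradient, and an LVEF distribution with mean 50 to 60 and SD 6 to 10 truncated at 45%. It falls to zero for a step at the median.

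A reader might infer that the primary result or the trial's stated power is weakened; neither is touched. Severity is low: a cheap improvement to an exploratory analysis.

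**What to change.** In SAP 9.3.1.3, before treatment codes are unblinded:

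1. Keep the Table 3-1 categories and their interaction p-values for the forest plot.
2. For the primary endpoint, add an LWYY model with treatment, continuous baseline LVEF and their product, with robust variance as in the primary analysis. The linear product term gives the test.
3. Add a restricted cubic spline version, with the number and placement of knots stated in advance, to plot the rate ratio and its 95% confidence interval across LVEF.
4. Optionally, do the same for log NT-proBNP, SBP, eGFR and age, labelled exploratory.

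The cost is two models and one figure for LVEF, and the same again for each optional covariate. No new data are needed. The downside is a few more exploratory tests without multiplicity adjustment. A linear term can also miss a non-monotone pattern or a threshold, which the spline and the retained categories would help show.

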3.2 Subgroup analyses

Subgroup analyses will be performed depending on the analysis purposes. Subgroups selected and types of analyses are specified in [Table 3-1](#) and will be detailed later in the sequel sections. In principle, there will be no adjustment for multiple comparisons for subgroup analyses.

4 Definitions of baseline, post baseline, analysis cut-off, and close-out

Single-blind run-in phase (Treatment run-in epoch)

The single-blind run-in phase (or run-in phase) is defined as the period between the start of the study drug (in general it should be Visit 101 or Visit 102) and the time prior to randomization (Visit 201). The run-in phase will be divided further into the valsartan run-in phase and the LCZ696 run-in phase. The start of the valsartan phase is the date the patient receives the run-in dose of valsartan. In principle, the day before a patient receives the first dose of LCZ696 (any dose level) will be the end of the valsartan run-in phase and the day the patient receives the first dose of LCZ696 will be the start day for the LCZ696 run-in phase for that patient. If the date of the start day of receiving LCZ696 is missing, then the date of Visit 103, which is the protocol specified run-in drug switching day, will be used as the start date for the LCZ696 phase. If the date of the last dose of valsartan run-in medication falls on the same day of the first dose of LCZ696 run-in medication, this day will be considered the end of the valsartan run-in phase and the following day will be considered as the start of the LCZ696 run-in phase. The LCZ696 run-in phase ends at the time when the patient receives the randomization drug. During these two run-in phases, patients will be on the run-in medications in a single blind manner.

Randomized treatment phase

The randomized treatment phase begins at the time of randomization and ends with the last study drug intake or the death of the patient, whichever comes earlier. During the randomized treatment phase, patients will return for scheduled clinic visits. For all related safety analyses randomized treatment starts with the first intake of randomized, double-blind study drug. Temporary discontinuation of the study drug will not be counted as randomized treatment phase discontinuation.

Post-randomized treatment phase

The post-randomized treatment phase (usually after unscheduled, permanent study drug discontinuation) begins after last study drug intake + 1 day and ends on the date last seen (or vital status confirmed by indirect contact).

Double-blind (DB) phase (Randomized treatment epoch)

The double-blind phase is the combination of the randomized treatment phase and the post-randomized treatment phase.

Baseline for run-in phase

The treatment run-in baseline is defined as the last available measurement prior to or at time of Visit 101 or Visit 102, whichever is earlier. For some parameters, values may be only collected at screening (Visit 1). For them the treatment run-in baseline will be at screening.

Baseline for double blind phase

The baseline for the double blind phase is defined depending on the parameter considered. In general, the baseline for the double blind phase is defined as the last available measurement during the LCZ696 *run-in* phase and randomization (generally Visit 199 or Visit 201). For the parameters that are not designated to have measurements collected during the LCZ696 run-in or randomization, the run-in baseline may be used as the baseline for the double blind phase. The following parameters will have the double blind phase baseline at randomization visit:

NYHA class, HF signs and symptoms, vital signs, waist/hip circumference, eGFR, safety laboratory values, endpoints, 1st morning urine (sub-study patients only), lab assessments, patient global assessment (it is assumed that patients will assess their health status comparing to that at randomization), KCCQ scores and EQ-5D assessments and MMSE.

The following parameters will have their double blind phase baseline measured only at screening visit (Visit 1), i.e., prior or at Visit 101 or 102:

Height, (HF, diabetes, liver, and other) medical histories, demography, echocardiogram, and inclusion/ exclusion criteria.

NT-proBNP will be collected in all patients at Visits 1, 101/102 (whichever occurs first), 103, 199/201, 203 and 205. Additional biological markers will be collected in a subset of patients. For these biomarkers, the baseline will be defined as values at Visit 101 or 102, whichever occurs first.

Unscheduled visit

Only for the analysis of safety laboratory evaluation will unscheduled measurements be taken into account. For efficacy evaluations, measurements from unscheduled visits will generally not be used, unless specifically specified.

Analysis cut-off date (Study endpoint for analysis)

The trial was designed to be terminated when 4600 patients have experienced a total of about 1847 confirmed primary composite events of heart failure hospitalization and CV death. If the assumptions of the study design were kept unchanged, the analysis cut-off date will be a predicted date when either the targeted 4600 patients have experienced 1847 primary composite events during a period of 2.42 years of enrollment plus 2.17 years of minimum follow-up or a study termination date has been decided based on other study termination decisions. Analysis cut-off date is determined to be Apr 30, 2019 based on prediction analysis.

Final visit

The final visit will be the last time a patient's study record has been taken. For a patient who is still alive and in the study the final visit will be his/her last clinical visit. For a patient who died or is determined to be lost to follow-up before the analysis cut-off date, the final visit will be his/her death/lost-to-follow-up day. For a patient who is alive but no longer has regularly scheduled clinic visits and whose study records only can be obtained by telephone or indirect contact, the final visit will be the day the study records being taken.

Close-out

Close-out is a final study period (about two-to-three months) consisting of arranging patients' final visits and completing study conduct, starting from the date (close-out date) when all the study sites are informed to schedule patients' final visits for those still alive. The close-out process will start before the analysis cut-off date. The final visit for each patient may occur prior to or immediately after the analysis cut-off date, depending on the timing the final visits can be scheduled in each site.

5 Missing date handling

Visit date missing

In any analysis or evaluation, if the visit date(s) is used but is missing, then the date(s) calculated based on the planned date(s) in the schedule specified in the protocol should be used to impute the missing date(s).

Event date missing or partially missing

If the date of an event is not known or is incomplete, the imputation rules are:

- a) If the day of the event is unknown, then the 15th day of this month will be imputed for a missing day;
- b) If only the month is unknown, then July will be used for imputation of the missing;
- c) If only the year of the event is known, then the 1st of July will be imputed for a missing day and month;
- d) The above rules are only for general case. If there is additional information available for the missing date, then the information should be used and the imputation of missing date should be treated differently. For example, if an event occurs between two visits and its date is missing, then the date in the middle of these visits may be used.

Medication stop date missing

If medication stop date is unknown or is incomplete, the imputation rules are:

- a) If only the day field of the drug stop is missing, then the missing date is imputed by using the 15th of the month;
- b) If year and month are missing, then use the next scheduled visit date (using the protocol specified visit schedule) from the previous last non-missing visit date to replace the missing drug stop date;
- c) If the drug stop date is completely missing, then:
 - a. If patient had fatal AEs (identified as either start or end date is equal to the date of death and the AE is flagged as an SAE), handling rules are (in the specified order):
 - i. AE end date is not missing: use the AE end date to replace the missing drug stop date;

- ii. AE end date is completely missing but AE onset date not missing: use the AE onset date to replace the missing drug stop date;
 - iii. AE end date is partially missing (only day field is missing): use Novartis standard procedure to impute the AE end date, and then use the imputed AE end date to replace the missing drug stop date;
 - iv. AE end date is completely missing and AE onset date is partial missing (missing the date field only): impute the AE onset date using Novartis standard procedure, and then use the imputed AE onset date to replace the missing drug stop date;
 - v. If both AE onset and end dates are completely missing, then use the last previous non-missing visit date plus 35 days to replace the missing drug stop date.
- b. If patients had no fatal AEs, handling rules are the same with the case where year and month are missing.

6 Subject disposition, background and demographic characteristics, medical history

